6.4.2 Sample Collection, Storage, and Shipping

Missed blood and urine samples should not be redrawn or recollected (unless the Investigator considers the sample necessary for subject safety) and should be noted as “not done” in source documentation along with a reason.

A central laboratory experienced in clinical research trials will be utilized. Collection, processing, storage and shipping procedures will be performed in accordance with the instructions provided by the central laboratory. Detailed instructions will be provided separately from this protocol in the laboratory manual. Blood and urine samples will be collected and analyzed for clinical laboratory tests. During the entire study, approximately 870 mL of blood will be drawn. Additional blood draws may be needed for any additional, unscheduled visits which are medically necessary.

Blood samples for measurement of certain clinical laboratory tests will be collected and shipped to the central laboratory. The central laboratory will ship the frozen specimens to the designated analytical facilities as detailed in the laboratory manual.

Samples are to be shipped to the central laboratory for each subject as visits are completed. The Investigator will provide a limited access, temperature monitored space for the study drug and a -80°C freezer space for respective serum and plasma aliquots.

6.4.3 Clinical Supplies

The sponsor or their assigned designee will supply vacutainers, blood collection tubes, needles, pipettes, labels, boxes with labels for storage of serum and plasma samples and all necessary shipping supplies/containers. The Investigator will supply all phlebotomy and centrifugation equipment including biohazard and/or safety supplies. The Investigator will ensure that all biohazard wastes are disposed of in accordance with Investigator site standard operating procedures (SOPs) and local regulations.

6.5 Dispensing Study Drug

The study coordinator (or designated site personnel) at the site will dispense the appropriate quantity of study drug to each subject, which will be recorded in the source document and on the appropriate eCRF.

6.6 Adverse Events Assessments

6.6.1 Definition

An AE is defined as any untoward medical occurrence in a subject regardless of its causal relationship to study treatment. An AE can therefore be any unfavorable and unintended sign (including an abnormal laboratory finding or symptom) or disease temporally associated with the use of a medicinal product whether or not considered related to the medicinal product.

6.6.2 Performing Adverse Events Assessments

The Investigator or designee will monitor each subject for clinical and laboratory evidence of AEs on a routine basis throughout the study. The Investigator or designee will assess and record

any AE in detail in the source document and on the appropriate eCRF including the date of onset, description, severity, duration, relationship of the AE to the investigational study drug, action(s) taken and outcome. AEs, whether in response to a query, observed by site personnel, or reported spontaneously by the subject will be recorded in the source document and on the appropriate eCRF.

6.6.3 AE Collection Period

All AEs that occur after the ICF has been signed must be reported in detail in the source document and in the appropriate eCRFs and followed to a satisfactory resolution, until the Investigator deems the event to be chronic or the subject to be stable, or until the subject's participation in the study ends.

Information to be collected includes description of the event (event term), date of onset, date of resolution, Investigator-specified assessment of severity and relationship to the investigational study drug, seriousness, as well as any required treatment or evaluations and outcome.

AEs resulting from concurrent illnesses, reactions to concurrent illnesses, reactions to concurrent medications, or progression of disease states must be documented as AEs. Pre-existing conditions (present before the start of the AE collection period) are considered concurrent medical conditions and should NOT be recorded as AEs, but must be documented in the medical history section of the eCRF and in the source document. However, if the subject experiences a clinically significant worsening or complication of such a concurrent condition, the worsening or complication should be recorded as an AE. Investigators should ensure that the AE term recorded captures the change in the condition.

Each AE should be recorded to represent a single diagnosis. Accompanying signs (including abnormal laboratory values) or symptoms should NOT be recorded as additional AEs. If a diagnosis is unknown, sign(s) or symptom(s) should be recorded as an AE(s). Changes in laboratory values are only considered to be AEs if they are judged to be clinically significant (ie, if some action or intervention is required or if the Investigator judges the change to be beyond the range of normal physiological fluctuation). If abnormal laboratory values are the result of pathology for which there is an overall diagnosis (e.g., increased liver enzymes in hepatitis), the diagnosis only should be reported as an AE.

Pre-planned procedures (surgeries or therapies) that were scheduled prior to the start of AE collection are not considered AEs. However, if a pre-planned procedure is performed early (e.g., as an emergency) due to a worsening of the preexisting condition, the worsening of the condition should be captured as an AE. Elective procedures performed where there is no change in the subject's medical condition (including thought processes around the reason for the elective procedure) should not be recorded as AEs, but should be documented in the subject's source document and captured in the source documentation and eCRF as procedures.

Any report of pregnancy identified for any female subject or for a female partner of a male subject should be reported immediately (within 24 hours of being informed) to the medical monitor. Pregnancies will be considered 'events of special interest' and will not be captured as serious adverse events (SAEs). The Pregnancy Report Form will be utilized to obtain BL and follow-up information. Pregnancies will be followed to termination or six weeks post-delivery

for determination of resolution to the event. Subjects who become pregnant during treatment must immediately be withdrawn from the study (classified as ET).

The Medical Dictionary for Regulatory Activities (MedDRA), Version 20.0 or later, will be used to code all AEs.

6.6.4 *Severity*

The intensity of the AE will be rated by the Investigator per Common Terminology Criteria for Adverse Events (CTCAE) version 5.0.

It should be noted that the clinical severity and seriousness of an AE are not synonymous, e.g., a severe headache is not classified as serious until it meets the required elements as an SAE.

The maximum severity attained for each AE reported will be recorded in the source documentation and in the appropriate eCRFs.

6.6.5 *Relationship*

The Investigator's assessment of an AE's relationship to the investigational study drug is not a factor in determining whether the AE is reported in the source documentation and the appropriate section of the eCRF. If there is any doubt as to whether a clinical observation is an AE, the event should be reported.

The relationship or association of the study drugs in causing or contributing to the AE will be characterized by the Investigator using the classifications and criteria outlined in [Table 3](#).

Table 3 Adverse Event Relationship Criteria

Relationship	Criteria
Not related	
• The temporal sequence of the AE onset relative to administration of the investigational product is not reasonable.• Disease or other drugs provide plausible explanations.• Dechallenge (if performed) is negative or ambiguous.
Unlikely related	
• The temporal sequence of the AE onset relative to the administration of the investigational product is reasonable.• Could also be explained by disease or other drugs.• Dechallenge (if performed) is positive or uncertain.• Rechallenge is negative.
Possibly related	
• The temporal sequence of the AE onset relative to administration of the investigational is reasonable.• Unlikely to be attributed to disease or other drugs.• Dechallenge (if performed) is positive.
Related	
• The temporal sequence of the AE onset relative to administration of the investigational product is reasonable.• Cannot be explained by disease or other drugs.• Dechallenge (if performed) is positive and pharmacologically/pathologically plausible.• Rechallenge (if feasible) is positive.• The AE shows a pattern consistent with previous knowledge of the investigational product or product class, i.e., pharmacologically or phenomenologically recognized/plausible or an objective and specific medical disorder.

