Subjects receiving treatment with calcitriol or another 1α -hydroxylated vitamin D analog, or if serum total 25-hydroxyvitamin D ≥ 30 ng/mL when taking vitamin D supplementation (including multivitamins and fish oil), will complete a 4-week washout period prior to BL assessments. Subjects will forgo further dosing with these none study medications for the duration of the study. Subjects receiving calcimimetic therapy within 12 weeks preceding screening will be ineligible for enrollment.

Blood samples will be collected from all subjects at weekly intervals during the screening and BL periods, during the 8-week treatment period, and at the specified times during the PK/CCI assessment. Key parameters to be analyzed in the collected samples include some or all of the following: serum calcifediol, CCI [REDACTED]

CCI [REDACTED]

[REDACTED]

VS and

AEs will be monitored at each study visit. Other parameters to be monitored less frequently include CCI [REDACTED] brief PEs and clinical laboratory tests (hematology and routine clinical chemistries).

Subjects will maintain a dietary intake during the study of approximately 1,000-1,500 mg of elemental calcium per day with dietary counseling and, as necessary, administration of a daily calcium supplement.

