3.3 Study Duration

This study is expected to be conducted in approximately 26 weeks from time of initial subject enrollment (first subject consented) to study completion for the last subject (last subject out/last visit complete). Subjects will participate in the study for up to approximately 14 weeks (1 week for screening, 4 weeks for washout (if required), 1 week for BL, and 8 weeks for treatment).

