For any information not available at the time of the first report that becomes available later, the Investigator should add this information to both the source documentation and the initial SAE section of the eCRFs, and provide any additional written documentation to the above number immediately or within 1 working day of receipt.

The sponsor or designee will notify the appropriate regulatory agencies of any serious and unexpected SAEs associated with the use of the investigational study drug according to regulations. Copies of any reports to regulatory agencies regarding serious and unexpected

SAEs will be provided to the Investigators by the sponsor or designee for review and submission to the IRB/EC.

If using a local IRB/EC, the Investigator is responsible for informing his or her IRB/EC per its requirements of any SAEs at that site. Copies of SAE correspondence with the IRB/EC, regulatory authorities, and other physicians must be provided to the sponsor's Clinical Services Department.

A subject experiencing one or more SAEs will receive treatment and follow-up evaluations by the Investigator, or they will be referred to another appropriate physician for treatment and follow-up. Withdrawal from the study and all therapeutic measures will be at the discretion of the Investigator at the site.

All SAEs will be followed until resolution or should the event become indistinguishable from the chronic disease condition, the subject will be followed for a minimum of 30 days after investigational study drug administration and subsequently all events will be closed. Pregnancies will be followed until six weeks following delivery to determine the outcome.

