6.6.8 Treatment-Emergent Adverse Events

A TEAE is defined as any AE with onset or worsening reported by a subject from the time that the first dose of study drug is taken in this study until 30 days following discontinuation of study drug administration.

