7.3 End of Study (EOS)

7.3.1 Visit 16 (Day 57) Last study visit (or Early Termination)

- Dosing compliance and dosing diary assessed for subjects assigned to CTAP101 Capsules and paricalcitol capsules plus low-dose cholecalciferol.
- Review of concomitant medications
- AE assessment
- PE (including weight, height and BMI)

- VS assessment
- Serum pregnancy test (for females of child bearing potential)
- Blood samples for the following analyses:
 - Chemistry (full panel) plus hematology

CCI

○ CCI calcifediol, CCI

CCI

CCI

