#### 3.3 Study Design

This is a phase 4, single- or multi-center, open-label study to evaluate the comparative safety, efficacy, and PK and **CCI** profiles of CTAP101 Capsules, IR calcifediol, high-dose cholecalciferol, and paricalcitol plus low-dose cholecalciferol **CCI** in male and female subjects at least 18 years of age with stage 3 or 4 CKD and VDI. The study will be conducted at up to 3 sites within the United States. Subjects (approximately 20 per arm) will receive the following treatments:

- 1) CTAP101 Capsules (30 mcg/capsule), 60 mcg by the oral route, once daily for 56 days;
- 2) Calcifediol IR (266 mcg/capsule), 266 mcg by the oral route, on Days 1 and 29;
- 3) Cholecalciferol (50,000 IU/capsule), 300,000 International Units (IU) by the oral route (6 capsules), on Days 1 and 29; and,
- 4) Paricalcitol (1 mcg/capsule) plus cholecalciferol (800 IU/capsule), 1 or 2 mcg plus 800 IU by the oral route, once daily for 56 days.

After 4 weeks of treatment, subjects who are receiving paricalcitol will double the dose to 2 mcg plus cholecalciferol 800 IU once daily in the morning before breakfast if all of the following conditions are met: the plasma iPTH has not decreased by at least 30% from

pretreatment BL and remains above 70 pg/mL, corrected serum total calcium is <9.8 mg/dL, and serum phosphorus is <5.5 mg/dL. Subjects who are receiving CTAP101 Capsules, IR calcifediol, or cholecalciferol (300,000 IU) will not undergo upward dose titration.

Subjects will reduce the dose of study drug per the following schedule if any of the following conditions are met: plasma iPTH is confirmed to be <30 pg/mL, corrected serum total calcium is confirmed to be >10.3 mg/dL, or serum phosphorus is confirmed to be >5.5 mg/dL.

Dose reduction (if needed):

CTAP101: decrease to 30 mcg per day (from 60 mcg per day)

IR calcifediol: hold Day 29 dose

Cholecalciferol 300,000 IU: hold Day 29 dose

Paricalcitol: decrease dose to 1 mcg per day (from 2 mcg per day)

Cholecalciferol 800 IU will not be adjusted

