## 9 SAFETY ANALYSIS

### 9.1 Adverse Events

Adverse events will be coded using MedDRA (Version 21.0 or higher). Each verbatim term will be mapped to a SOC and PT. Severity grades for safety parameters will be assigned using the Common Terminology Criteria for Adverse Events (Version 5.0). When changes in the severity of an AE occur more frequently than once a day, the maximum severity for the experience that day will be noted.

Treatment-emergent AEs (TEAE) are events with onset dates and times on or after the administration of the first dose of study drug and within 30 days after the last dose of study drug, or a continuing AE diagnosed before the date of the first dose of study drug, which increases in frequency, severity, or character during the course of the study.

An overall summary of TEAEs will be provided for the safety population summarizing subjects with at least 1: TEAE, related TEAE, grade 3, 4, or 5 TEAE, serious TEAE, related serious TEAE, TEAE leading to study discontinuation, or related TEAE leading to study discontinuation as well as the number of events within each of the previously mentioned categories by treatment.

In addition, summaries of unique TEAEs will be presented for the safety population by SOC, PT, and by treatment and overall, and will include the number and percentage of subjects who experience the unique event for:

1. All TEAEs,
2. All TEAEs by relationship,
3. All TEAEs by severity grade,
4. All TEAEs leading to study discontinuation,
5. All serious TEAEs, if more than 1 serious TEAE is recorded.

Related TEAEs include all those classified by the investigator as possibly related or related. Unrelated TEAEs are those events classified as not related or unlikely related.

For summaries by relationship, the most related event will be selected. For summaries by severity, the most severe grade will be selected.

Multiple events will be counted only once per subject and treatment in each of the previously mentioned summaries by treatment and overall. In the presentation, SOC and PT will be sorted in alphabetical order.

All AEs captured in the database will be presented in by-subject data listings; however, only TEAEs will be summarized.

MedDRA version will be provided in a footnote in both tables and data listings.

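### Both documents run the treatment-emergent AE window to 30 days after the last dose, but no AE contact is scheduled after Day 57, so in the daily arms 29 of those 30 days have no scheduled ascertainment

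*Protocol*

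**What the plan says.** **The window.** Protocol 6.6.8 starts the TEAE period at the first dose and extends it "until 30 days following discontinuation of study drug administration". SAP 9.1 uses the same limit: "within 30 days after the last dose of study drug".

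**The observation.** Protocol 3.1 states that "AEs will be monitored at each study visit". Protocol 7.3.1 is titled "Visit 16 (Day 57) Last study visit (or Early Termination". The schedule of events in Protocol Appendix 1 and SAP Table 1 both end at that column. Protocol 3.3 builds up to about 14 weeks of participation from "1 week for screening, 4 weeks for washout (if required), 1 week for BL, and 8 weeks for treatment", with no follow-up period after treatment.

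**Follow-up of known events.** Protocol 6.6.3 has a reported AE followed to resolution, until it is judged chronic or the subject stable, "or until the subject's participation in the study ends". For SAEs, 6.6.7.3 requires follow-up to resolution. For an SAE that can no longer be told apart from the chronic disease, it says "the subject will be followed for a minimum of 30 days after investigational study drug administration and subsequently all events will be closed". Pregnancies are followed until six weeks after delivery.

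**Dosing.** SAP 3.3 gives CTAP101 as "60 mcg by the oral route, once daily for 56 days", and paricalcitol plus low-dose cholecalciferol for the same 56 days. IR calcifediol and high-dose cholecalciferol are given on Days 1 and 29.

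**The concern.** A window that defines which events count is useful only if someone looks for events throughout it. Here the definition reaches a month past the last dose, while planned observation stops on Day 57 whatever the date of the last dose. In the daily arms dosing continues almost to that visit, so nearly all of the post-dose month falls after the last contact. A new event in that month would reach the database only if the subject happened to report it.

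The month is not empty of drug. Protocol 3.2 reports a terminal half-life of about 30 days for calcifediol after repeated CTAP101 dosing, with steady state not reached at 6 weeks and attained after 12. After 8 weeks of dosing, exposure should be near its highest when observation stops. AEs are a primary safety endpoint (Protocol 2.2.3), and comparing safety across the four arms is among the study's principal aims (Protocol 3.2).

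In addition, 6.6.3 allows follow-up of a non-serious AE still ongoing at Day 57 to stop there.

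**Working it through.** **Inputs**
- Last visit: Day 57 (Protocol 7.3.1 and Appendix 1).
- TEAE limit: last dose + 30 days (Protocol 6.6.8, SAP 9.1).
- Last planned dose, daily arms: Day 56, from the 56 days of dosing in SAP 3.3. The protocol does not name the day.
- Last planned dose, monthly arms: Day 29.

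**The plan's own figures first**
- SAP 7.2 places the Day 57 sample 28 days after the Day 29 dose: 57 − 29 = 28. Agrees.
- Participation: 1 + 4 + 1 + 8 = 14 weeks. Agrees, and leaves nothing for follow-up.

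**Coverage of the 30 post-dose days**

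Window end = last dose day + 30. Days observed = min(30, 57 − last dose day).

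| Case | Last dose | Window ends | Days observed | Share unobserved |
|---|---|---|---|---|
| Daily arms, as planned | Day 56 | Day 86 | 1 of 30 | 29/30 = 96.7% |
| Monthly arms, as planned | Day 29 | Day 59 | 28 of 30 | 2/30 = 6.7% |
| Monthly arms, Day 29 dose held | Day 1 | Day 31 | 30 of 30 | 0% |
| Daily arm, drug stopped Day 43, visits continue | Day 43 | Day 73 | 14 of 30 | 16/30 = 53% |
| Daily arm, a dose also taken on Day 57 | Day 57 | Day 87 | 0 of 30 | 100% |

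CTAP101 is taken at bedtime. If the Day 57 visit falls 8 to 12 hours after the last dose (an assumption), the unobserved share is 1 − (12/24)/30 = 98.3% to 1 − (8/24)/30 = 98.9%.

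**Whole TEAE period, in days elapsed since Day 1**
- Daily arms: (57 − 1)/(86 − 1) = 56/85 = 65.9% observed.
- Monthly arms: (57 − 1)/(59 − 1) = 56/58 = 96.6% observed.

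**Calcifediol remaining at the end of the window**

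With a half-life of about 30 days and simple exponential decline, 0.5^(30/30) = 50% of the drug-related rise would remain 30 days after the last CTAP101 dose.

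**Where the current rule changes counts within Days 1 to 57**

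For subjects who dose as planned, every event up to Day 57 lies inside both windows (Day 59 and Day 86), so the rule removes nothing. If the Day 29 dose is held, the window closes on Day 31 and new events on Days 32 to 57 are collected but not counted as TEAEs. The same happens in a daily arm if the last dose is before Day 27, since the window then closes before Day 57.

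**The case against.** The strongest reply is that the 30-day limit only classifies reported events and does not promise active surveillance, so this is a mismatch of wording. Several parts of that case stand:

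- No sentence says that AE collection ends on Day 57. The clause in 6.6.3 governs how long a reported AE is followed. The Day 57 end comes from reading 3.1, 3.3, 6.6.3, 7.3.1 and Appendix 1 together.
- A reader might infer from 1 of 30 against 28 of 30 days that the TEAE comparison favours the daily arms. The documents do not support that. All arms share the same visit schedule from Day 1 to Day 57. The 28 days in the monthly arms are also not time off treatment: the SAP sets the dosing interval there at 28 days, so they are the second dosing interval.
- A reader might infer that the tables claim 30 days of follow-up. No TEAE table title in SAP Appendix A mentions 30 days.
- A reader might cite Appendix 2 on hypercalcaemia lasting about 4 weeks after calcifediol is stopped. That text concerns long-term use of the immediate-release product and the persistence of an existing abnormality. It is not evidence of new events missed after 8 weeks of CTAP101.
- A reader might infer that nothing present at Day 57 is followed. Protocol 6.6.7.3 does provide for known SAEs and pregnancies.
- Safety analysis is descriptive only (Protocol 9.10).

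The reply does not remove the gap. A limit 30 days past the last dose has almost no content in the daily arms if nobody asks about that month, and spontaneous reporting is not systematic ascertainment. The SAE clause covers events already identified and does not detect new ones. For a daily-arm completer it can also run to Day 86, after participation has ended.

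**Conclusion.** The point holds as a gap between the stated window and the planned observation. It does not show bias in the between-arm comparison to Day 57. For subjects who complete dosing as planned, 29 of the 30 post-dose days in the daily arms have no scheduled AE ascertainment, against 2 of 30 in the monthly arms. New events after daily dosing ends would be largely missed, and non-serious AEs ongoing at Day 57 need not be followed.

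The figures assume a last daily dose on Day 56 and a last visit on Day 57. They change with early stopping, suspension or a held dose, as shown above. The half-life argument applies to CTAP101; the documents give no half-life for paricalcitol. Results up to Day 57 remain valid, so this should be corrected but does not undermine the study.

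**What to change.** 1. **Add one contact.** In Protocol 6.6.3, 7.3 and Appendix 1, schedule one AE/SAE telephone contact 30 days after the last dose: about Day 86 in the daily arms and Day 59 in the monthly arms for subjects who dose as planned. Cost: one call per subject and one schedule entry, with completion 86 − 57 = 29 days (about 4 weeks) later in the daily arms. A call will not detect events visible only in laboratory results, and the protocol should say so.

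2. **Fix the comparison window.** In SAP 9.1, base the between-arm TEAE tables on first dose to Day 57 (Visit 16/ET) in every arm, whatever the date of the last dose, and tabulate later events separately by days since last dose. This needs wording and programming only. It leaves counts unchanged for subjects who dose as planned, and brings in observed events now excluded when the Day 29 dose is held or daily dosing stops early.

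3. **Fallback.** If no contact is added, end the TEAE definition at Visit 16/ET in both Protocol 6.6.8 and SAP 9.1. This makes the text match the conduct but recovers no post-treatment information.

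4. **Reconcile.** State how the 30-day SAE follow-up in 6.6.7.3 fits with the end of participation in 6.6.3.

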1.5 Secondary Hyperparathyroidism

SHPT is a condition commonly associated with CKD in which the parathyroid glands secrete excessive amounts of PTH. SHPT affects 40% to 82% of patients with stage 3 or 4 CKD [Levin et al 2007] and frequently arises as a result of either VDI or impaired kidney function, both of which can prevent sufficient production of vitamin D hormone to properly regulate calcium and phosphorus metabolism and PTH secretion. Impaired kidney function can also cause elevated serum phosphorus and fibroblast growth factor 23 (FGF23) which exacerbate SHPT. SHPT requires prompt and effective treatment, as prolonged elevation of PTH causes excessive calcium and phosphorus to be released from bone, leading to metabolic bone disease and calcification of cardiovascular and renal tissues. In the absence of effective treatment, SHPT becomes progressively more severe and unresponsive to treatment [Nigwekar et al 2014].

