9.10.1 Primary Endpoints Analyses

9.10.1.1 Adverse Events

All AEs will be collected on the eCRF and coded via SOC and preferred term using MedDRA version 20.0 or higher. Additionally, the intensity of all AEs will be coded using CTCAE v. 5.0. AEs with missing onset date will be treated as TEAEs and missing onset date will be imputed as the date of Visit 1, unless the event end date indicates that the event resolved prior to Visit 1, in which case it will be documented in medical history. AEs with partial onset date will be treated as TEAEs unless the partial onset date or end date of the event is complete enough to indicate that the event started or resolved prior to the administration of the investigational study drug, in which case it will be documented in medical history. Detailed information collected for each TEAE will include: AE number, a description of the event, start date, end date or ongoing as of date, outcome, therapy for event, whether the AE is serious, seriousness criteria (life-threatening, death, hospitalization/prolongation of hospitalization, congenital anomaly, persistent or significant disability/incapacity, required intervention to prevent permanent impairment/damage), severity, and relationship to the study drug. The incidence of the AEs will be summarized by population subgroup for all TEAEs, potentially drug-related TEAEs, serious TEAEs, discontinuation due to TEAEs, TEAEs by relationship to study drug (definite, probable, possible, unrelated) and TEAEs by severity (mild, moderate, severe). The number and percentages of subjects with a TEAE will be summarized by SOC and preferred term and presented overall and by population subgroup. TEAEs will be sorted in descending order of total incidence of SOC and preferred term within each SOC. The percentages will be based on the number of Safety subjects in a particular population subgroup. If a subject has more than one TEAE that code to the same preferred term, the subject will be counted only once for that preferred term. Similarly, if a subject has more than one TEAE within a SOC category, the subject will be counted only once in that SOC category. All AEs collected on the eCRF will be included in the listings. An additional listing of all subject deaths will also be provided.

Diagnostic procedures will be collected separately in the eCRF and coded via SOC and preferred term using MedDRA version 20.0 or higher in a manner similar to AEs.

9.10.1.2 *Vital Signs*

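### Protocol Table 3 gives an adverse event that both drug and disease could explain no clear place above 'Unlikely related', and SAP 9.1 counts that grade as unrelated, so related-TEAE counts may be understated

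*Protocol*

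**What the plan says.** Protocol 6.6.5 asks the investigator to grade whether study drug caused an event or contributed to it, using the four grades of Table 3. Three entries in that table matter here:

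- 'Unlikely related' covers an event with reasonable timing that "Could also be explained by disease or other drugs". Its other bullets are "Dechallenge (if performed) is positive or uncertain" and "Rechallenge is negative".
- 'Possibly related' requires the event to be "Unlikely to be attributed to disease or other drugs".
- 'Related' is stricter still: "Cannot be explained by disease or other drugs".

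SAP 9.1 splits the four grades in two. 'Possibly related' and 'related' count as related; for the rest, "Unrelated TEAEs are those events classified as not related or unlikely related". The split feeds the counts of related TEAEs, related serious TEAEs and related TEAEs that led to discontinuation.

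Protocol 9.10.1.1 plans its summary on another scale: "TEAEs by relationship to study drug (definite, probable, possible, unrelated". SAP 9.3 counts hyperphosphatemia as drug-related without saying how relatedness is decided.

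**The concern.** Table 3 has no clear related grade for mixed causation, although 6.6.5 asks about contribution as well as cause. A drug that contributes implies that something else contributed too, and the table places that case below the SAP's cut.

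The population makes this more than a formality. Every subject has stage 3 or 4 CKD, and Protocol 1.5 says "Impaired kidney function can also cause elevated serum phosphorus and fibroblast growth factor 23 (FGF23) which exacerbate SHPT". Protocol 5.3.1 lists raised phosphorus and raised calcium among the effects of excess study drug. Calcium supplements may be prescribed (5.5.1), so other treatment can also be an explanation. Section 5.3 calls for dose reduction or suspension on confirmed laboratory values, phosphorus among them, so dechallenge information will arise for these events. Under Table 3, a positive result does not by itself lift the grade.

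At stake is the attribution part of the safety report: the three related counts, and the drug-related hyperphosphatemia endpoint if Table 3 is used to apply that label.

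**Working it through.** The plan gives no figure on this point, so there is none to reproduce. The check sets the texts side by side, enumerates the cases and adds a labelled illustration.

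**Step 1: the rows as written.** I assume that an event must meet every bullet in a row, and that a bullet qualified by 'if performed' or 'if feasible' is waived when the test was not done. Table 3 does not state its rule.

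| Grade | Timing | Disease or other drugs | Dechallenge | Rechallenge | SAP 9.1 |
|---|---|---|---|---|---|
| Not related | not reasonable | plausible explanation | negative or ambiguous, if done | no bullet | unrelated |
| Unlikely related | reasonable | could also explain | positive or uncertain, if done | negative (no qualifier) | unrelated |
| Possibly related | reasonable | unlikely cause | positive, if done | no bullet | related |
| Related | reasonable | cannot explain | positive and plausible, if done | positive, if feasible | related |

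**Step 2: enumerate.** Fix timing as reasonable and let disease be able to explain the event. Cross dechallenge (positive, uncertain, negative, not performed) with rechallenge (positive, negative, not performed): 4 × 3 = 12 combinations.

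| Reading of the rechallenge bullet | Unlikely related | No category | Possibly related or Related |
|---|---|---|---|
| Literal: must be negative | 3 | 9 | 0 |
| Taken as 'if performed' | 6 | 6 | 0 |

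Positive dechallenge with positive rechallenge, the strongest evidence of a drug effect, fits no row on either reading. These are counts of combinations, not frequencies of events. Some combinations are formal only, since a rechallenge presupposes that dosing was stopped.

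**Step 3: one case.** A stage 4 subject's phosphorus rises on study drug and falls when dosing stops; dosing is not restarted. Read literally, no row fits, because there was no negative rechallenge. With 'if performed' understood, the event is 'Unlikely related' and the SAP tables it as unrelated. It reaches 'Possibly related' only if the investigator judges kidney disease an unlikely cause.

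**Step 4: possible size.** Let n = 20 per arm (SAP 3.1), p the share of subjects with a drug-caused TEAE, and s the share of those whose drug-caused events disease could all explain. If every such event is graded below 'Possibly related' or left unplaced, the expected number counted as related is n × p × (1 − s). Both p and s are assumptions; the documents give neither.

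| p | s = 0 | s = 0.5 | s = 1 |
|---|---|---|---|
| 0.10 | 2.0 | 1.0 | 0 |
| 0.23 | 4.6 | 2.3 | 0 |
| 0.43 | 8.6 | 4.3 | 0 |

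Example: 20 × 0.23 × (1 − 0.5) = 2.3. At p = 0.10, the chance that an arm shows no related subject goes from 0.90^20 = 0.122 at s = 0 to 0.95^20 = 0.358 at s = 0.5. The loss is total only if disease could explain every drug-caused event.

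**The case against.** The best reply is that the table leaves room for judgement. That an event could be explained by disease is a statement of possibility; that disease is an unlikely cause is a statement of likelihood. Both can be true. After a positive dechallenge an investigator may reasonably judge disease unlikely and choose 'Possibly related'. This stands, and it is why the counts *may* be understated rather than *are*. It does not close the gap: the same event can be graded either way, in an open-label study.

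Several stronger readings are tempting, and the documents do not support them:

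- *Any event that disease could explain is 'Unlikely related'.* The unqualified rechallenge bullet means that many such events strictly fit no row.
- *Renal impairment can always explain a rise.* Protocol 1.5 says that it can cause raised phosphorus. It does not say always, and that sentence does not cover calcium. Entry requires phosphorus below 5.5 mg/dL and corrected calcium below 9.8 mg/dL (inclusion criterion 5) and bars phosphate binders, so a new rise is not automatically a disease effect.
- *Drug effects disappear from the safety report.* SAP 9.1 tabulates all TEAEs, including by relationship and by severity. SAP 9.2 summarises laboratory changes and shifts, and SAP 9.3 counts hypercalcemia from laboratory values with no causality filter. Attribution is affected; occurrence is not.
- *Expedited reporting is affected.* All serious events go to the sponsor within 24 hours whatever their grade (6.6.7.3), and that section does not tie later regulatory reporting to Table 3 or to the SAP's split.
- *The earlier programme shows the bias.* Protocol 1.9 mentions four hyperphosphatemia cases, none judged related, but gives neither the scale used nor the reasons.

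On the scale mismatch, Protocol 9.4 leaves planned analyses to the SAP, and SAP 9.1 uses the Table 3 terms. The list in 9.10.1.1 is therefore an inconsistency with little analytic effect, though it still cannot be filled from the grades collected.

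**Conclusion.** The point holds in limited form. With reasonable timing, an event that disease or other drugs could also explain has no clear place above 'Unlikely related', even after a positive dechallenge. SAP 9.1 then counts it as unrelated, so the three related counts may be understated. Drug-related hyperphosphatemia may be understated too, on the condition that Table 3 is what applies that filter. Table 3 also leaves dual-cause events with a positive rechallenge, or with none, strictly without a grade, and its terms do not match Protocol 9.10.1.1.

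The size is unknown. It depends on the share of drug-caused events that disease could explain and on how investigators use their discretion. The finding that no combination reaches a related grade rests on reading every bullet as required. The safety analysis is descriptive, so no test is affected. The change is worth making because the rule blurs attribution for an event type that the plan names as an endpoint.

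**What to change.** 1. **Table 3.** Place events with reasonable timing, a possible disease or other-drug explanation and a positive dechallenge under 'Possibly related'. Remove the positive result from the 'Unlikely related' dechallenge bullet, amend the disease bullet of 'Possibly related' so that the rows do not conflict, and add 'if performed' to the rechallenge bullet. On the grid above, this gives 3 combinations 'Possibly related', 4 'Unlikely related' and 5 still unplaced (three with a negative dechallenge, two with a positive rechallenge but no positive dechallenge). Table 3 should therefore also say what to do when no row fits exactly.
2. **SAP 9.1.** Tabulate the four grades in separate columns, and give the related counts both without and with 'unlikely related'. This is better than redefining related as everything except 'not related', which would contradict the grade's own label.
3. **Protocol 9.10.1.1.** Replace the list of relationship terms with those of Table 3.
4. **SAP 9.3.** Report hyperphosphatemia from laboratory values regardless of attribution, with the drug-related subset shown separately and its rule stated.

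The cost is wording and some extra table columns; the four grades are collected anyway. Related percentages will be higher and less specific, which showing both cuts makes visible. Dechallenge is easier to observe in the two daily arms than in the two dosed only on Days 1 and 29, so item 1 alone could raise related counts unevenly; item 2 guards against that. If grading has already begun under the present table, items 2 and 4 can still be adopted before database lock.
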